16.0 Protocol Adherence

The approved Clinical Investigational Plan/Protocol for the FRED study shall be followed without deviation. If the Principal Investigator and/or sponsor believe that an amendment or modification to the protocol is necessary, such amendment or modification shall be presented, in written form, to the study Primary Investigator, [name], and The Board for review and approval.

The process for handling protocol violations/deviations is described in the Manual of Operating Procedures.

17.0 Protocol Amendments and Modifications

Administrative changes which do not affect the risk/benefit ratio to the Subject shall be presented to the Investigation Site IRB/EC for abbreviated approval, according to the IRB policies in place at that institution. Any such changes shall be submitted to the Sponsor for record-keeping purposes. Material amendments or modifications shall require the full review and approval of the Primary Investigator, The Board, the IRB/EC at each Investigation Site, the FDA and the Sponsor prior to any implementation.

Any amendments or modifications, whether deemed administrative or material, to the original Clinical Investigation Plan/Protocol shall be shared with all Investigation Sites.

18.0 Risks and Benefits

As stated in the background section of this protocol, there are clinical challenges in treating intracranial wide neck aneurysms and there are several alternatives for the treatment of wide-neck intracranial aneurysms. Surgical approaches include clipping and trapping or wrapping. Endovascular treatment of intracranial aneurysms with detachable coils, which was introduced in 1996, allowed for an alternative therapeutic option to surgical clip ligation. Despite the introduction of improved coils as well as stent and balloon assisted coiling, there still some limitations: incomplete aneurysm occlusion as well as recurrence in complex large and giant aneurysms. If left untreated, aneurysms can rupture, causing death or significant permanent morbidity.

With an endovascular approach, detachable coils placed within the aneurysm sac of wide-neck aneurysms may protrude into the parent vessel and compromise normal blood flow. Thus, this anatomical configuration makes it difficult to achieve a thorough packing of the aneurysm with coils. As such, the rates of complete angiographic occlusion for these wide-neck aneurysms are often very low when standard techniques are employed.

With the stent-assisted technique, the neurovascular stent is placed across the aneurysm neck, to act as a bridge to prevent coils from protruding into the parent artery. Stenting may allow the operator to more safely achieve a higher packing density of coils. These more thoroughly packed aneurysms are likely better protected against future re-canalization and rupture. In addition, these devices placed in the parent vessel may produce an anatomical and physiological "remodeling" of the parent artery giving rise to the aneurysm. These effects may improve the rates of complete aneurysm occlusion and enhance the durability of the treatment.

The FRED System is designed as an alternative to embolization by coiling alone, stent-assisted coiling, or clipping of wide-necked aneurysms. Based on the concept of flow diversion stents, the FRED System is designed to preserve intraluminal blood flow through the parent artery and adjacent perforating vessels while occluding/redirecting blood flow into the aneurysm, allowing thrombosis to occur in the aneurysm. Adjunctive use of embolic coils may also be practiced. Due to its smaller cell size resulting from a higher metal-to-surface area ratio, the FRED is typically used without the adjuvant therapy of coils placed within the aneurysm sac of the parent artery, normally associated with a coil assist stenting techniques.

Some of the potential adverse events and risks/complications that may be associated with intracranial stenting with the FRED System include those listed in the Adverse Events section of this protocol. Mitigation activities including mechanical, performance, biocompatibility and sterilization testing have been performed with the FRED System and all tests met the applicable acceptance

criteria. Animal testing showed that the FRED System could be safely deployed and implanted in rabbit carotid arteries.

The efficacy of the FRED System for use with embolic coils for the treatment of unruptured, wide neck (neck \geq 4 mm or dome to neck ratio $<$ 2), intracranial, aneurysms arising from a parent vessel with a diameter \geq 2.0 mm and \leq 5.0 mm has not been demonstrated. However, the benefit of using the flow diversion stenting technique to prevent aneurysm rupture may outweigh the identified risks.

19.0 Control of Investigational Devices

The investigational devices (FRED System) shall be the sole responsibility of the Principal Investigator at the investigational site.

They shall be stored in a secure location that is separate from any other devices.

The investigational devices shall only be utilized in accordance to the FRED study protocol.

The accountability of each device that is delivered to the Investigation Site, including size, length, expiration date, lot number, and quantity, shall be solely the responsibility of the Principal Investigator.

The Principal Investigator shall not provide the investigational devices assigned to the FRED study to any other person, under any circumstances.

The process for maintaining investigational device accountability is found in the Manual of Operating Procedures.

20.0 End of Study

20.1 Expected Study End

The study will close once the desired number of subjects has been enrolled and the 12 months follow-up period or primary endpoint has been reached for all subjects. Study duration is estimated to be approximately 36 months from the enrollment of the first subject.

20.2 Early Study End

The study may be terminated early for any of the following reasons:

- New findings invalidate the positive risk-benefit assessment;
- The time schedule and recruitment phase cannot be met, secondary to low recruitment;
- In response to recommendations by the Data Safety Monitoring Board (DSMB);
- The sponsor decides to terminate the study, secondary to device related issues.

20.3 Termination of a Site by the Study Sponsor

The study may be terminated at an individual investigational site due to significant lack of compliance to the approved Clinical Investigational Plan/Protocol. The site may also be closed due to lack of enrollment. This will be determined by the study sponsor in consultation with The Board.

20.4 Resumption of Terminated Sites

The sponsor shall not resume the study at a terminated investigational site without prior IRB/EC and FDA approvals.

21.0 Publication

Any potential journal publications about the FRED study shall be provided to the sponsor for review prior to submission for publication consideration, as stated in the Site Investigator Protocol Agreement. The FRED study will be posted on the clinicaltrials.gov website.

1 SUMMARY

Title	Pivotal Study of the MicroVention, Inc. Flow Re-Direction Endoluminal Device Stent System in the Treatment of Intracranial Aneurysms
Preface	
This Statistical Analysis Plan (SAP) describes the planned analysis and reporting for protocol CL12001 (Pivotal Study of the MicroVention, Inc. Flow Re-Direction Endoluminal Device Stent System in the Treatment of Intracranial Aneurysms.). This study is being completed to assess the safety and effectiveness of the FRED for the treatment of intracranial aneurysms.
 
The following documents were reviewed in preparation of this SAP:
 
 • Clinical Research Protocol CL12001 rev 4, issued September 27, 2016

	
 • Annotated eCRF Live v1.0 dated 19Apr2016 • FDA Presubmission Q140977
Purpose	The purpose of this SAP is to prospectively outline the planned analyses to be completed to support the completion of the Clinical Study Report (CSR) for protocol CL12001. The planned analyses identified in this SAP will be included in regulatory submissions and future manuscripts. Any post-hoc, exploratory analyses completed to support planned study analyses, which were not identified in this SAP, will be documented and reported in appendices to the CSR.
Device Name And Intended Use	The device is called FRED (Flow Re-Direction Endoluminal Device) is indicated for the endovascular treatment of adults harboring intracranial aneurysms with a high likelihood for failure or recurrence with conventional techniques including wide-necked or geometrically complex intracranial aneurysms (including fusiform aneurysms) in the anterior and posterior cerebral circulation.
Primary Endpoints	
The primary effectiveness endpoint is successful aneurysm treatment with the FRED Device as defined by complete occlusion utilizing the Raymond scale of the target aneurysm and $\leq 50\%$ stenosis of the parent artery at the target IA at 12 months as assessed by angiography and in whom an alternate treatment of the target IA has not been performed within 12 months post-FRED Device placement.
 
The primary safety endpoint is death or major stroke within 30 days post procedure, or neurological death or major ipsilateral stroke within 12 months post-procedure.

Secondary Endpoints	
Secondary endpoints described in the protocol are listed below:
 
 1) Proportion of subjects with clinically acceptable (90-100%) occlusion of the target aneurysm, $\leq 50\%$ stenosis of the parent artery at the target IA at 12 months (+ 60 days, -30 days). as assessed by angiography, and in whom an unplanned alternative treatment of the target IA had not been performed within 12 months 2) Proportion of subjects in whom an unplanned alternative treatment of the target IA had not been performed within 12 months 3) Proportions of subjects with clinically acceptable aneurysm occlusion (90 %-100 %) of the target aneurysm at 12 months (+ 60 days, -30 days). 4) Incidence of $\geq 50\%$ In-Stent Stenosis (ISS) at the target IA at 12 months as assessed by angiography at an independent corelab 5) Proportion of subjects with complete occlusion of the target aneurysm on 12-month angiography (+ 60 days, -30 days). 6) Incidence of FRED System procedure related Serious Adverse Events 7) Incidence of FRED System device-related Serious Adverse Events; 8) Incidence of unsuccessful delivery of the FRED system implant; 9) Incidence of unsuccessful deployment of the FRED flow-diverter intra-cranial stent 10) Incidence of migration of the FRED system implant at 12 months; 11) Unplanned alternative treatment on the target IA within 12 months, defined as re-treatment of the target aneurysm with an alternative treatment modality including open repair, endovascular placement of an additional stent or treatment of In-stent Stenosis observed at the 180 day or 12 month follow-up time-points or at an unscheduled study follow up visit. 12) Change in clinical and functional outcomes at 180 days and 1 year follow up, as measured by an increase in the modified Rankin Scale compared to baseline; 13) Incidence of major stroke, as measured by NIHSS at 12 months (and ophthalmic examination related to the target aneurysm if determined appropriate.

	14) Incidence of minor stroke, as measured by NIHSS at 12 months (and ophthalmic examination related to the target aneurysm if determined appropriate..
Study Design	
A multi-center, prospective, single-arm study with follow-up at discharge, 30 days (± 7 days), 180 days (± 30 days) and 12 months (+ 60 days, -30 days). Data will be analyzed according to nominal visit, e.g. 30 days, 180 days, 12 months as opposed to actual date.
 
The intent-to-treat (ITT) population as defined below will be the primary population for all efficacy analyses and the safety population for all safety analyses. One hundred forty-five (145) subjects will constitute the ITT cohort, which is identical to the Safety cohort. These subjects were enrolled and treated at 23 sites located in United States and Japan.
 
Subjects are included in study analyses consistent with the prospective literature control, with efficacy and safety objective performance criteria (OPCs) used to determine sample size.
 
Two OPC sets will be considered in support of efficacy and safety as per the original protocol (primary) as well as more strict (supportive) OPCs as follows:
 
 • Primary: Original PG specified in the protocol (45% for efficacy and 25% for safety) • Supportive: Updated PG presented to FDA at the Feb 2017 meeting (46% for efficacy and 15% for Safety). 
Study success is defined as achieving statistical significance for the primary OPCs.
 
Primary Analyses: The powers will be 80% to rule out a 45% OPC (efficacy) margin (lower bound) and 80% to rule out a 25% OPC (safety) margin (upper bound) using one-sided tests. The trial will be considered successful if the one-sided 95% credible lower bound of the efficacy rate exceeds the 45% OPC and the one-sided 95% credible upper bound of the safety rate is below the 25% OPC. The use of one-sided testing is consistent with the protocol.
 
Supportive Analyses: The powers will be 90% to rule out a 46% OPC (efficacy) margin (lower bound) and 90% to rule out a 15% OPC (safety) margin (upper bound) using two-sided tests. The trial will be considered successful if the two-sided 95% credible lower bound of the efficacy rate exceeds the 46% OPC and the two-sided 95% credible upper bound of the safety rate is below the 15% OPC. The use of two-sided testing is consistent with the PIPELINE PMA and FDA guidance.

Follow-Up Schedule	All enrolled and treated subjects had follow up scheduled at 30 day (± 7 days), 180 days (± 30 days), and 12 months (+ 60 days, -30 days).
Interim Analyses	No interim analysis are planned.
Final Analyses	
This SAP covers analyses planned for the FRED trial, designed to investigate the safety and efficacy of the FRED during the course of treatment and through 12 months following treatment.
 
All analyses identified in this SAP relate to subject data up to and including the 12-month follow-up visit. Any post-hoc, or unplanned, analyses not identified in this SAP will be clearly identified in the CSR.

2 PROSPECTIVE STUDY OVERVIEW

FRED is a single-arm pivotal study in the treatment of intracranial aneurysms in which subjects will be implanted with FRED. Current common therapies, such as surgical or endovascular approaches, are not able to treat intracranial aneurysms with wide necks effectively. Currently in the US, there is one flow diverter, the Pipeline Embolization Device (PED), approved by FDA and there are currently three CE Mark approvals for Pipeline, SILK and the NeuroEndoGraft.

Subjects enrolled into the study and treated with FRED shall be followed at discharge and 30 days, 180 days and 12 months. A subject considered enrolled but not treated because of a failed FRED deployment because of issues related to the procedure shall be closely monitored for one (1) week. If the device entered the blood stream and the subject has an Adverse Event, that subject will have the 30-day, 180 days and 12-month clinical follow-ups. If the FRED Device enters the blood stream and cannot be deployed secondary to technical issues with the device itself (e.g., FRED Device malfunction or failure to access the target site due to the FRED Device), the Subject will be counted as enrolled with intent-to-treat. This will be considered as a secondary endpoint failure. The Subject will be maintained within the study and will not be replaced by another Subject. If the FRED device never entered the subject's bloodstream that subject will be excluded from all the analysis populations. No additional analysis is planned for data collected beyond 12 months study follow up period.

This study incorporates the use of an independent blinded Clinical Events Committee (CEC) which reviewed and adjudicated all the primary and secondary safety outcome measures of the study, as well as all the adverse events and technical events reported in the study. In addition, independent blinded Data Safety and Monitoring Board which provided study safety and efficacy oversight reviewed all the site-reported and CEC adjudicated clinical data of the FRED study, and an independent angiographic core laboratory determined aneurysm occlusion and the degree of device stenosis reported by the investigational sites.

2.1 STUDY ASSESSMENTS

All subjects enrolled into the study and treated with the FRED shall be followed as stated in the study protocol, at discharge and 30 days (± 7 days), 180 days (± 30 days), and 12 months (+60 days, -30 days):

1. Discharge interval shall include a clinical and neurological evaluation
2. 30-day follow-up shall include a clinical and neurological evaluation
3. 6-month follow-up shall include a clinical, neurological and angiographic evaluation
4. 12-month follow-up shall include a clinical, neurological and angiographic evaluation

3 STUDY OBJECTIVES AND ENDPOINTS

3.1 STUDY OBJECTIVE

The objective of this study is to evaluate the safety and effectiveness of the MicroVention FRED System when used in the treatment of wide-necked intracranial aneurysms.

3.2 PRIMARY ENDPOINTS

Primary Safety Endpoint:

The primary safety endpoint is the proportion of subjects who experience one or more of the following:

- a. death or major stroke within 30 days post procedure
 - b. neurological death or major ipsilateral stroke within 12 months post procedure
- ✦ *A major stroke is defined as a new neurological event that persists for > 24 hours and results in a ≥ 4 -point increase in the NIHSS score compared to baseline or compared to any subsequent lower score.*
 - ✦ *A major ipsilateral stroke is defined as that occurring within the vascular distribution of the stented artery*
 - ✦ *Neurologic death is defined as a death which has been adjudicated by the independent clinical events committee to have directly resulted from a neurologic cause*

Primary Effectiveness Endpoint:

Proportion of subjects with complete occlusion of the target aneurysm utilizing the Raymond Scale and $\leq 50\%$ stenosis of the parent artery at the target IA at 12 months as assessed by angiography and in whom an alternative treatment of the target IA had not been performed within 12 months post-FRED placement; where an alternative treatment is defined as re-treatment of the target aneurysm with an alternative treatment modality including open repair, endovascular placement of an additional stent or treatment of In-stent Stenosis observed at the 180 day or 12 month follow-up time-points or at an unscheduled study follow up visit.

3.3 STUDY SUCCESS

Study success is defined as establishing the one-sided 95% credible bounds (primary) for both the safety and efficacy endpoints according to the respective OPCs.

3.4 SECONDARY ENDPOINTS

Secondary endpoints described in the protocol are listed below:

1. Proportion of subjects with clinically acceptable (90-100%) occlusion of the target aneurysm, $\leq 50\%$ stenosis of the parent artery at the target IA at 12 months (+ 60 days, - 30 days), as assessed by angiography, and in whom an unplanned alternative treatment of the target IA had not been performed within 12 months

2. Proportion of subjects in whom an unplanned alternative treatment of the target IA had not been performed within 12 months
3. Proportions of subjects with clinically acceptable aneurysm occlusion (90 %-100 %) of the target aneurysm at 12 months (+ 60 days, -30 days).
4. Incidence of $\geq 50\%$ In-Stent Stenosis (ISS) at the target IA at 12 months as assessed by angiography at an independent corelab
5. Proportion of subjects with complete occlusion of the target aneurysm on 12-month angiography (+ 60 days, -30 days).
6. Incidence of FRED System procedure related Serious Adverse Events
7. Incidence of FRED System device-related Serious Adverse Events;
8. Incidence of unsuccessful delivery of the FRED system implant;
9. Incidence of unsuccessful deployment of the FRED flow-diverter intra-cranial stent
10. Incidence of migration of the FRED system implant at 12 months;
11. Unplanned alternative treatment on the target IA within 12 months, defined as re-treatment of the target aneurysm with an alternative treatment modality including open repair, endovascular placement of an additional stent or treatment of In-stent Stenosis observed at the 180 day or 12 month follow-up time-points or at an unscheduled study follow up visit.
12. Change in clinical and functional outcomes at 180 days and 1 year follow up, as measured by an increase in the modified Rankin Scale compared to baseline;
13. Incidence of major stroke, as measured by NIHSS at 12 months (and ophthalmic examination related to the target aneurysm if determined appropriate).
14. Incidence of minor stroke, as measured by NIHSS at 12 months (and ophthalmic examination related to the target aneurysm if determined appropriate).

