A supplement analysis was also conducted to identify the in-stent stenosis rate (3.8%) to ensure that this event is not underreported across multiple publications. A 12% core lab adjustment was added when calculating the OPC for publications which did not include a core lab when reporting on aneurysm occlusion. The combined estimate for effectiveness for the anterior circulation (15 articles) was 56.2% (95% CI 42.8, 69.6) leading to a 45% one-sided lower 95% confidence limit for the anterior location. The combined estimate for effectiveness for the posterior location (9 articles) was 40.1% (95% CI 17.8, 62.3) leading to a 21.4% one-sided lower 95% confidence

limit for the posterior location. The sample size for the anterior circulation was 1120 vs. 81 for the posterior circulation.

Study Differences:

The current study will assess both anterior and posterior lesions following treatment. The combined anterior and posterior OPC from the FRED literature analysis document for both safety and efficacy is not directly comparable to that used for Pipeline since the PED was only used to treat ICA segments up to the superior hypophyseal segment whereas the FRED target is multiple vessel segments in the anterior and posterior circulation. The FRED study expects to up to 80% in the anterior circulation and up to 20% in the posterior circulation.

The Pipeline PUFs Study had a different primary safety endpoint which was the proportion of subjects who experienced either death due to neurologic causes or major ipsilateral stroke by 180 days after the last IA treatment procedure whereas the FRED Study primary safety endpoint is the proportion of subjects who experience one or more of the following: death or major stroke within 30 days post procedure and neurological death or major ipsilateral stroke within 12 months post procedure. Thus the primary safety endpoints are different. The 20% OPC used in the PUFs Study is likely too low given the longer duration.

OPC Selection Criteria:

The OPC for efficacy is motivated by our literature analysis where a 45% OPC was estimated to be the 95% lower bound determined from a series of qualifying publications. This estimate was based on a mixture of anterior and posterior lesions.

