2. Proportion of subjects in whom an alternative treatment of the target IA had not been performed within 12 months
3. Proportions of subjects with clinically acceptable aneurysm occlusion (90 %-100 %) of the target aneurysm at 12 months (+ 60 days, -30 days)
4. Incidence of $\geq 50\%$ In-Stent Stenosis(ISS)at the target IA at 12 months as assessed by angiography at an independent corelab

5. Proportion of subjects with complete occlusion of the target aneurysm on 12-month angiography(+ 60 days, -30 days)
6. Incidence of FRED System procedure related Serious Adverse Events
7. Incidence of FRED System device related Serious Adverse Events;
8. Incidence of unsuccessful delivery of the FRED device
9. Incidence of unsuccessful deployment of the FRED device
10. Incidence of migration of the FRED device at 12 months
11. Unplanned alternative treatment on the target IA within 12 months defined as re-treatment of the target aneurysm with an alternative treatment modality including open repair, endovascular placement of an additional stent or treatment of In-stent Stenosis observed at the 180 day or 12 month follow-up time-points or at an unscheduled study follow up visit.
12. Incidence of change in clinical and functional outcomes at 180 days and 1 year follow up, as measured by an ≥ 3 point increase in the modified Rankin Scale due to neurologic disability as compared to baseline
13. Incidence of major stroke, as measured by NIHSS at 12-months (and ophthalmic examination related to the target aneurysm if determined appropriate)
14. Incidence of minor stroke, as measured by NIHSS at 12-months (and ophthalmic examination related to the target aneurysm if determined appropriate)

The statistical analyses of the primary and secondary endpoints of the study will be based on imaging data that has been reviewed and assessed by an independent core lab and on trial clinical data that has been reviewed and adjudicated by the independent Clinical Events Committee (CEC).

Study Success Criteria:

The criterion for success is based on the posterior probability of the alternative hypotheses for both efficacy and safety (i.e. both efficacy and safety being met).

Efficacy Criterion

The FRED System will be declared efficacious if the posterior probability of the alternative hypothesis H_A based on the primary efficacy endpoint for is large, that is

$$P(H_A|Data) = P(\pi_e > 45\%|Data) > \pi^*$$

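### SAP 3.4 item 4 scores in-stent stenosis on the 12-month angiogram alone, so a stenosis found at 180 days and treated can be reported as event-free

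*SAP*

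**What the plan says.** **In-stent stenosis.** SAP 3.4 item 4 (also in the SAP 1 summary) is the incidence of ≥50% "In-Stent Stenosis (ISS) at the target IA at 12 months as assessed by angiography at an independent corelab". Protocol 5.5 item 4 is worded the same way.

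**Occlusion.** Item 3 is "Proportions of subjects with clinically acceptable aneurysm occlusion (90 %-100 %) of the target aneurysm at 12 months" and item 5 is "Proportion of subjects with complete occlusion of the target aneurysm on 12-month angiography". Neither carries a retreatment condition.

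**Retreatment.** SAP item 1 adds "and in whom an unplanned alternative treatment of the target IA had not been performed within 12 months", item 2 is "Proportion of subjects in whom an unplanned alternative treatment of the target IA had not been performed within 12 months", and item 11 is "Unplanned alternative treatment on the target IA within 12 months, defined as re-treatment of the target aneurysm with an alternative treatment modality". Item 11's list covers open repair, an additional stent, and treatment of in-stent stenosis observed at 180 days, at 12 months or at an unscheduled visit. The primary effectiveness endpoint (SAP 3.2) gives the same list for alternative treatment without the word *unplanned*. Protocol 5.5 item 2 also omits it: "Proportion of subjects in whom an alternative treatment of the target IA had not been performed within 12 months".

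**Handling rules.** Protocol 6.2 makes retreatment a failure for the primary effectiveness endpoint only. SAP 6.6 and 7.3 deal with missing data. SAP 7.6 counts events among evaluable subjects under a Beta(1,1) prior. None of these says how a retreated subject is scored on items 3 to 5. SAP 7.6.1 plans no formal hypothesis tests for the secondary endpoints.

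**The concern.** Angiography is scheduled at both 180 days and 12 months, and the plan's own definition of alternative treatment foresees that a stenosis seen at 180 days may be treated. A successful treatment then removes that case from the 12-month reading. The endpoint is named an incidence, and a reader will take it as how often the device led to ≥50% stenosis in the first year. What it delivers is how often such a stenosis was present at month 12, after any treatment for it.

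The sponsor took care over this event in its literature work: Protocol 5.1 describes a supplementary analysis of in-stent stenosis "to ensure that this event is not underreported across multiple publications". The trial's own rate should meet the same standard. At stake is a descriptive safety and durability figure, reported with a credible interval, that will be read as device performance at one year.

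**Working it through.** The documents give no rate, power or sample size for items 1 to 5 or 11, so there is no planned figure to reproduce. The size below is an illustration under the SAP's own model.

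**Inputs**
- Literature in-stent stenosis rate: 3.8% (Protocol 5.1). No stenosis threshold or follow-up time is attached to it.
- n = 145, the ITT cohort in the SAP 1 summary. SAP 7.2 also gives 140.
- Model: posterior Beta(1 + Y, 1 + n − Y), equal-tailed 95% interval (SAP 7.6).
- Number treated before month 12 and reading below 50% at month 12: not in the documents, so varied from none to all.

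**Expected cases.** 0.038 × 145 = 5.5, so 5 or 6 subjects. Starting from 6:

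| Treated and <50% at month 12 | Counted by item 4 | Rate | 95% credible interval |
|---|---|---|---|
| 0 | 6/145 | 4.1% | 1.9% to 8.7% |
| 1 | 5/145 | 3.4% | 1.5% to 7.8% |
| 2 | 4/145 | 2.8% | 1.1% to 6.9% |
| 3 | 3/145 | 2.1% | 0.8% to 5.9% |
| 4 | 2/145 | 1.4% | 0.4% to 4.9% |
| 5 | 1/145 | 0.7% | 0.2% to 3.8% |
| 6 | 0/145 | 0.0% | 0.0% to 2.5% |

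Each such subject lowers the rate by 1/145 = 0.7 points. With n = 140, 0.038 × 140 = 5.3, and the range is 5/140 = 3.6% (1.6% to 8.1%) down to 0/140 (upper limit 2.6%).

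**Can the rate be recovered elsewhere?**
- Item 11 pools open repair, additional stents and treatment of in-stent stenosis.
- The summary and Kaplan-Meier curve in SAP 9.3 concern retreatment of the target aneurysm and are not split by reason.
- The component display in Protocol 6.2 defines its stenosis component at 12 months as well.

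None of these gives the number of subjects with ≥50% in-stent stenosis at any scheduled reading.

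**Items 3 and 5.** A retreated subject raises these rates by 0.7 points only if the aneurysm was not occluded before retreatment and is occluded at 12 months. Three such subjects would add 3/145 = 2.1 points and seven would add 7/145 = 4.8 points. These counts are assumptions; the documents give no retreatment rate.

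**Items 1, 2 and 11.** Set side by side, item 11's definition of unplanned alternative treatment and the primary endpoint's definition of alternative treatment list the same interventions at the same time points. Nothing separates planned from unplanned.

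**The case against.** The strongest reply is that treated stenosis is not hidden. Such a subject fails the primary effectiveness endpoint and falls within item 11. Stenosis of the stented segment is a listed anticipated device effect (Protocol 13.2), and adverse events are adjudicated and tabulated (SAP 8). Item 4 also states its time point openly, no secondary endpoint is tested, and the intervals in the illustration overlap heavily. All of this stands, and it limits the weight of the point. It does not supply a core-lab rate of ≥50% stenosis over the year, which is what an incidence promises.

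Three stronger readings are tempting and are not supported.

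- **A planned-retreatment loophole.** A reader might infer that a retreatment booked after the 180-day angiogram could be called planned and counted as success in items 1, 2 and 11. Item 11's own definition covers treatment of stenosis observed at 180 days. Protocol 5.5 item 1 uses the terms with and without *unplanned* interchangeably, and the protocol synopsis also has the word. What remains is an inconsistent, undefined qualifier.
- **Occlusion credited to the device.** A reader might infer that items 3 and 5 report retreated aneurysms as occluded by FRED. They state the aneurysm's status at 12 months and attribute it to nothing. They stand beside the primary endpoint and item 1, which carry a retreatment condition. Replacing them with a rule that any alternative treatment means not occluded would go too far. It would score an aneurysm that the device had occluded as not occluded when only in-stent stenosis was treated, and it would largely duplicate item 1 and the primary endpoint.
- **A threat to study success.** Success rests on the two primary endpoints, and the effectiveness endpoint already excludes subjects with any alternative treatment.

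**Conclusion.** Item 4 as written can understate the occurrence of ≥50% in-stent stenosis, because treatment after the 180-day angiogram can turn an event into a non-event. The direction favours the device. The size is small in absolute terms: at the 3.8% literature rate, the reported figure lies between about 4% (upper limit 8.7%) and 0% (upper limit 2.5%). This rests on two assumptions: that 3.8% applies to this definition and population, and that treated cases read below 50% at 12 months. If no case is treated before month 12, treatment causes no distortion.

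For items 3 and 5 the gap is a missing companion figure. For items 1, 2 and 11 it is a matter of consistent wording, and no bias is shown.

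**What to change.** 1. **Item 4.** Define an event as core-lab in-stent stenosis of ≥50% on the 180-day or the 12-month angiogram, or any treatment of in-stent stenosis through the 12-month evaluation. Show the 12-month-only figure beside it, so that stenosis that was treated or had regressed by month 12 is visible as the difference.
2. **Items 3 and 5.** Keep the as-observed 12-month status. Add a second rate in which subjects whose aneurysm was retreated by another modality (open repair or an additional stent, not treatment of in-stent stenosis alone) count as not occluded.
3. **Items 1, 2 and 11.** Delete *unplanned*, so that the wording matches the primary endpoint and Protocol 5.5 item 2.

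The cost is SAP wording and a few table lines. Images from 180 days and 12 months already go to the core laboratory (Protocol 5.11 and 12.2.2), and retreatment is already summarised (SAP 9.3). Unscheduled angiograms are left out of the core-lab criterion because the protocol records them on a case report form and does not specify core-lab reading; a stenosis found there and treated is still caught by the treatment criterion. The downside is a slightly less favourable descriptive rate. The change should be made before outcomes are analysed, since SAP 9.4 has later additions described as post hoc.
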